SOCIAL/BEHAVIORAL/EDUCATIONAL RESEARCH PROTOCOL

UNIVERSITY OF MISSOURI

Project Title: A Next Generation, Low Cost Tracking System for Healthcare Process Validation

IRB Number: 2016906

Version Number: 4

Version Date: 02/22/2021

Principal Investigator: [name]

Funding Source: NIH-NINR and GaN Corporation

I. Research Objectives/Background

The purpose of the project is to develop a new way to understand patient care data analytics by using a real-time location system (RTLS). We will deploy the RTLS-based nursing activity analysis system at an ICU at the University Hospital, University of Missouri Health Care in Columbia, Missouri. We will validate location system performance against manual observation of nursing activity. We will correlate nursing activity metrics against patient outcomes as measured by Sequential Organ Failure Assessment (SOFA) score.

Real-Time Location Systems (RTLS) identify and locate tagged assets, staff, or patients as they move through a hospital. RTLS can address a variety of other practical problems in healthcare such as inventory management and patient tracking and monitoring. Most RTLS employ some flavor of Radio Frequency (RF) angle-of-arrival, time-of-flight, time-difference-of-arrival, or Received Signal Strength Indicators (RSSI). However, these techniques have several significant disadvantages. Among these are confusion from multipath and environmental clutter, line-of-sight operation, need for synchronization, range restrictions, and expense. Furthermore the human body, composed mainly of salt water, occults high frequency signals making fading a serious problem. Wi-Fi tracking, in particular is, limited to an accuracy of 10-20ft and cannot provide the precision data required for high-fidelity applications in healthcare such as workflow management.

In the current study, we will validate location system performance against manual observation of nursing activity. We will correlate nursing activity metrics against patient outcomes as measured by SOFA score. The anticipated outcome is actionable, location-based data to describe, analyze, or validate healthcare processes with a maximum error of 5% relative to manual observation. Also, we will identify specific location-based metrics useful in monitoring nursing activity. We will deploy and test the system in a medical ICU at the University Hospital ICU. The anticipated outcome is a real-time statistical quality control chart capable of monitoring nursing processes and detecting anomalies with user-configurable statistical power.

II. Recruitment Process

Prospective participants will receive an individual email from co-investigator explaining study including the need for participants willing to wear two location tags for the duration of their shift. The Informed Consent form and Demographic Question will be attached to this email. Those willing to participate will also be asked to send the completed Demographics Questionnaire attached to their email response. Receipt of the completed Demographics Questionnaire will signify their consent to participate.

The co-investigator will explain in the individual email that this study is to solely gain knowledge regarding their workflow as they deliver patient care and is not an evaluation of their performance or clinical judgment. Their participation in the study will not be revealed to their manager unless the participant wishes. The co-investigator will explain that participation is voluntary, they can withdraw at any time without risk to their employment and all aspects of their participation will be confidential.

III. Consent Process

A Waiver of documentation of consent form will be attached to the individual's email as well as the Demographic Questionnaire. The Waiver of Documentation of Consent form will provide an overview of the study. They will be informed both in the form and in the text of the email that the return of the completed Demographic Questionnaire signifies their consent to participate in the study and that participation is voluntary and confidential. They will be provided with the co-investigator's contact information should they have questions or concerns.

In addition, information from the EMRs of patients assigned to the nurse participants will be abstracted retrospectively under the Waiver of Consent after the patients have been transferred from the ICU. Patient factors will be used to help interpret the nurse participant data. However, concurrent patient data abstraction is not necessary for data analysis in this research project as there will be no intervention introduced that would impact the patient data. Further, patients in this ICU are usually unable to provide informed consent due to the presence of mechanical ventilation and continuous sedation.

IV. Inclusion/Exclusion Criteria

Inclusion criteria include English speaking, RN or LPN licensure.

Exclusion criteria include nurses helping to provide care but not having a patient assignment and nurse managers.

V. Number of Subjects

The study design is prospective, observational. The subject population is medical intensive care unit (ICU) nurses at University Hospital, MU Health Care. The anticipated number of subjects is 20. Normally, there are 10 nurses in each ICU per day shift (7:00 AM – 7:30 PM). During the data collection, the research team will monitor one designated medical ICU for 4 months (80 observation days).

VI. Study Procedures/Study Design

Recruited nurses will receive two RTLS location tags prior to their shift from trained undergraduate industrial and manufacturing systems engineering (IMSE) students who will keep a log of the nurses' name and tag identification. The nurses will carry the tags for the duration of their shift and then return the tags to the students. While they carry the RTLS tags, IMSE students will stand at the corner of the nurse's station in each pod to record the nurses' activities and the time spent in these activities using a data collection form previously developed during earlier pilot work when IMSE students collected time-motion data regarding ICU nursing care activities. If any special events occur during the observation period, they will record a description of these events, which include but not be limited to unscheduled medical activities or admission of a new patient to the ICU from the Emergency Department (ED). The RTLS location tag distribution and nurse observation will occur four to five days per week until a total of 80 days of location and observation data is obtained. For each patient that is assigned to an observed ICU nurse, data will be extracted retrospectively from their EMR. The abstracted data will include: age, gender, hospital admitting diagnosis, medical ICU admitting diagnosis, past medical diagnoses, laboratory values occurring during, or 24 hours prior to observation time, neurological status, mean arterial pressures during observation time, intravenous medications administered during observation time, any diagnostic studies performed outside of the ICU during the observation time, and any in-room procedures performed during the observation time.

VII. Potential Risks

There is minimal risk to the participants in this study. There are no potential risks or discomfort for the participant as there will be no change in their work process. Methods to avoid inadvertent coercion in the recruitment process will be deployed.

VIII. Anticipated Benefits

Analyzing the ICU nurse's workflow can furnish an understanding of the causes of delayed and missed care delivery. The findings from this research will highlight opportunities to improve the workflow management design. Such information can guide future workflow management to reduce the ICU nurse's workload and the risk of delayed or missed care in the ICU resulting in improved patient outcomes.

IX. Compensation

Each participant will be given a gift card (\$10). If they participate multiple times, then they will receive multiple gift cards. For example, if a nurse participates this study on five day shifts, then he or she will receive a five \$10 gift cards.

X. Data Safety Monitoring Plan

The data to be collected in this research project is from observation and tracking of the participants' movements using location tracking technology as they engage in their normal work routine. The Principal Investigator (PI) will provide data and safety monitoring through the following processes:

1. Each participant will be assigned a study code by the co-investigator (Co-I). A key linking the participant to their study code will be kept in an electronic file that is stored in an account that has a HIPAA-compliant security rating and can only be accessed by the PI and Co-I.
2. The username used to access the study subject's electronic medical record event log data will be removed from the data and replaced with the subject's study code by the principal investigator and the co-investigator. Only de-identified event log data will be used in the analysis.
3. Informatics specialists will de-identify patient data using the Safe Harbor method and assign a unique code to each patient's data. They will export the deidentified data to a secure account provided by the University of Missouri for data analysis. Only research team members will have access to this account. To anticipate the possible need to re-identify the patient, the informatics specialists will export a key connecting the medical record number with the unique code to a separate account that has a HIPAA-compliant security rating and can only be accessed by the PI and Co-I.
4. The first case and every tenth subsequent case will be reviewed by the PI and Co-I for compliance with IRB requirements and conformance with informed consent requirements.
5. Weekly research team meetings to review the data collected and resolve any issues encountered during the data collection session
6. A log will be kept whereby the research team member distributing the location tags to the participants for the data collection session will enter the tag identification number; the co-investigator will enter the study code of the subject receiving the tag into the same log. In the event that there is an issue with the signal produced by the tag, the tag will be removed from service and substituted with another using the same log entry procedure. The removed tag will be inspected and tested by the PI and/or manufacturer. It will only be returned to service if the issue is resolved. Such events will be reported to NINR by the PI.
7. We will monitor the test on at least a daily basis looking for potential adverse events in compliance with existing The University Hospital policies and procedures. Adverse events may include:
 - a. Adverse patient outcomes attributable to the test
 - b. Statistically significant changes in patient outcomes
 - c. Any other unanticipated problems with the study
8. We will provide details to NINR and the IRB, including:
 - a. Details of the event
 - b. Any recommendations arising out of the study
 - c. Any actions taken as a result of a potential adverse event
9. As per the University of Missouri Health Sciences Institutional Review Board (IRB) Core Standard Operating Procedure for Event Reporting and the Standard Operating Procedure for Unanticipated Problems, the Principal Investigator will be responsible for:
 - a. Reporting to the University of Missouri Health Sciences IRB within 5 business days of the investigator becoming aware of unanticipated problems that meet all of the following criteria:
 - i. **unexpected** (in terms of nature, severity, or frequency) given (a) the research procedures that are described in the protocol-related documents, such as the IRB-

approved research protocol and informed consent document; and (b) the characteristics of the subject population being studied;

- ii. **related or possibly related** to participation in the research (possibly related means there is a reasonable possibility that the incident, experience, or outcome may have been caused by the procedures involved in the research); and
- iii. suggests that the research places subjects or others at a **greater risk of harm** (including physical, psychological, economic, or social harm) **than was previously known or recognized.**

- b. Unanticipated problems reported to the University of Missouri Health Sciences IRB will be done using the IRB's Case Report Form
- c. The Principal Investigator will maintain a log, database, or other tracking system for trends

10. Potential adverse events may include:

- a. Data privacy violations: Our HIPAA-compliant plan will anonymize personal data and store it in a secure fashion, so a data privacy problem is unlikely
- b. Electromagnetic Interference (EMI): [name] employed an earlier generation of tracking devices that showed exhibited no interference or incompatibility with other ICU electronic devices. However, the researchers will be alert to the potential problem and remove any interfering tags from service

XI. Multiple Sites

NA

XII. References

NA

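### Does the 5% accuracy target for the location system fail because the observers' own error is never measured?

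*Protocol*

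**What the plan says.** Section I gives as the first task: "We will validate location system performance against manual observation of nursing activity". The only numeric target, also in Section I, is presented as an anticipated outcome: location data on "healthcare processes with a maximum error of 5% relative to manual observation". No alpha, power, pass/fail rule or summary statistic is attached to it.

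Section VI describes both sides of the comparison. On the system side, "Recruited nurses will receive two RTLS location tags prior to their shift", and the nurses carry them until the shift ends. On the reference side, "IMSE students will stand at the corner of the nurse's station in each pod", noting what each nurse does and for how long on a form from earlier pilot work. The form is not reproduced. The number of students per pod, the sight lines and any double observation are not stated.

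Two other sources could bear on where a nurse was. Section VI has patient record data that include "any diagnostic studies performed outside of the ICU during the observation time". Section X, item 2, on coding the nurses' usernames, shows that record event logs will be used: "electronic medical record event log data will be removed from the data and replaced with the subject's study code". Neither is tied to the validation.

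**The concern.** If error is defined relative to the observer, the whole difference is charged to the location system. The tag moves with the nurse and the student does not, and Section VI itself expects procedures inside rooms and studies off the unit. If students fail to record time when a nurse is away from the post, an accurate system would look inaccurate. If both sources err in the same direction, an inaccurate system could look acceptable.

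The two tags appear to offer a way out, but a bias common to both never appears in their difference. Section I warns of radio-frequency systems that "the human body, composed mainly of salt water, occults high frequency signals making fading a serious problem", and two tags on one body may share that influence.

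At stake is the study's only quantitative accuracy statement, and through it the use of the data to check care processes and run a control chart. Whatever is not captured during the 80 observation days would be hard to recover afterwards.

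**Working it through.** **Inputs.** From the Protocol: the 5% target (Section I) and a shift from 7:00 AM to 7:30 PM (Section V), which is 12.5 × 60 = 750 minutes. The 5% has no derivation, so there is no planned figure to reproduce. The Protocol gives no observer error, system error or correlation between tags; every such value below is an assumption.

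**1. Identifiability.** Let b be the system's relative bias and o the observers'. The observed relative difference is D = (1 + b)/(1 + o) − 1. Setting D = +5% gives b = 1.05(1 + o) − 1:

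| Assumed o | b giving D = +5% |
|---|---|
| −10% | −5.5% |
| −5% | −0.25% |
| 0 | +5% |
| +5% | +10.25% |

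All four pairs produce the same observation. More data do not separate them: with an assumed mean difference of 6% and SD of 5%, the mean stays at 6% while its standard error falls from 1.1 points (n = 20) to 0.18 points (n = 800). This part of the concern is correct.

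**2. Size if time goes unrecorded.** With a perfect system and u unrecorded minutes, D = u/(750 − u):

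| u (min) | Logged total (min) | D |
|---|---|---|
| 15 | 735 | 2.0% |
| 30 | 720 | 4.2% |
| 60 | 690 | 8.7% |

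D reaches 5% at a missed fraction of 0.05/1.05 = 4.76%, and 0.0476 × 750 = 35.7 minutes.

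**3. Would that loss be hidden?** The middle column answers this. Students record durations while the tags are worn, and the shift length is known. An hour unrecorded leaves a log of 690 minutes against 750. The reason for the gap may be unclear, but its amount is visible. Time logged under the wrong activity would leave no such gap, but that is a different error from the one quantified here.

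**4. The masking case.** A system bias of +10% with observers at +5% gives 1.10/1.05 − 1 = 4.8%, within the target. On the shift-total basis of step 2 this means 750 × 1.10 = 825 and 750 × 1.05 = 787.5 minutes inside a 750-minute shift, which cannot happen. The example works only for time per activity, and on that metric 36 minutes is not the break-even. The two illustrations therefore cannot be combined into one estimate of size.

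**5. Two tags.** With true SDs of 4% (system) and 2% (observer) and tag-error correlation ρ, the two-tag estimates are 4√(1 − ρ) and √(2² + ρ × 4²). At ρ = 0 these give 4.0 and 2.0; at ρ = 0.5, 2.8 and 3.5; at ρ = 0.9, 1.3 and 4.3. Shared tag error would be credited to the observers. But all three inputs are assumed, and the Section I remark on body blocking belongs to a list of drawbacks of existing techniques. It does not describe how this system behaves.

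**6. What the possible changes would achieve.**
- *Marking out-of-view intervals on the form.* The form may already do this. All-time agreement would remain the main result, with the same ambiguity.
- *Fixing a summary measure, denominator and clustered interval for the 5%.* This is normally left to the statistical analysis plan, which is not shown.
- *Duplicate observation.* Sixteen shifts on 16 nurses would give the inter-observer SD to within about 0.74 to 1.55 times its estimate. Two students at one post share the same blind spots, so the systematic part stays unmeasured.

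**The case for a change.** The strongest case for a change is that the weakness lies in data capture, which an analysis plan cannot repair. The post is fixed, the nurses are expected to work in rooms and off the unit, and nothing written says how that time is handled. Training and a piloted form may reduce observer error but do not measure it. Adding a field to a form costs very little, and the data are meant to support checks on care processes, which need more than a match with a stationary student.

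Part of this stands. The Protocol does not measure observer error, and a difference should not be read as system error alone. The cost argument is also fair. Three things weaken the rest. No statement in the Protocol shows that a student's view is obstructed, since there is a post in each pod and the layout is not described. The supposed omission concerns a form that the reader cannot see. And the cheap step would show where the two sources diverge without saying which is wrong; that would take an independent reference or a different vantage point. The record data give only a partial check, since an off-unit study locates the patient and not necessarily the nurse.

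**Conclusion.** No change is needed. It is true that one difference cannot separate two biases, but that holds for every two-method comparison without a third reference. The Protocol's wording already limits the claim to agreement with observers; that it treats them as error-free is an inference. The one figure anchored in the Protocol, about 36 of 750 minutes, assumes that out-of-view time goes unrecorded, and such a loss would show as a shortfall in logged time. The other magnitudes rest on observer biases, SDs and tag correlations that the Protocol does not give.

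What remains is a matter of interpretation that analysts can be expected to handle: report the 5% as agreement with manual observation, check logged totals against shift length, and do not attribute a difference to the location system alone. This conclusion assumes that students log durations across the period the tags are worn, as Section VI describes. It would be weaker if the unseen form recorded only selected activities or part of the shift.

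### Does timing the record abstraction after ICU transfer restrict the SOFA analysis to patients who survive the ICU?

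*Protocol*

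**What the plan says.** The aim at stake is stated in Section I of the protocol: "We will correlate nursing activity metrics against patient outcomes as measured by SOFA score".

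Section III (Consent Process) covers the patient records. Its population is "information from the EMRs of patients assigned to the nurse participants", and these data "will be abstracted retrospectively under the Waiver of Consent after the patients have been transferred from the ICU". The reason offered is that "concurrent patient data abstraction is not necessary for data analysis in this research project", because nothing in the study intervenes on patients.

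Section VI (Study Procedures/Study Design) states whose records are used: "For each patient that is assigned to an observed ICU nurse, data will be extracted retrospectively from their EMR". Several of the listed items are tied to the observed shift, for example "laboratory values occurring during, or 24 hours prior to observation time".

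Section IV (Inclusion/Exclusion Criteria) deals with nurses only: "Exclusion criteria include nurses helping to provide care but not having a patient assignment and nurse managers". Section X (Data Safety Monitoring Plan), item 7a, lists "Adverse patient outcomes attributable to the test" among the events to be looked for.

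**The concern.** Transfer is the only trigger that Section III names for reading records under the waiver, and death in the ICU is not mentioned. Taken word for word, the condition is never met for a patient who dies there. Section VI promises data on every assigned patient, so the two sections seem to disagree.

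If the literal reading governed, the stakes would be real. SOFA measures organ failure, so losing ICU deaths removes patients by severity and trims the upper end of the outcome. If nursing activity also affects the risk of death, inclusion would depend on a common effect of the two variables being correlated, which can bias the correlation either way. It might also seem that patients still in the ICU at the end of data collection would be lost, and that deaths would vanish from the records reviewed for adverse outcomes.

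**Working it through.** **Step 1: is the clause about who or about when?**

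| Place in the protocol | What it fixes | Condition on survival or transfer? |
|---|---|---|
| Section III, population | patients assigned to participating nurses | none |
| Section III, transfer clause | the time at which records are read | transfer named; death not mentioned |
| Section III, reason given | why abstraction need not be concurrent | none; concerns timing only |
| Section IV, exclusions | which nurses take part | none; no patient criteria |
| Section VI, extraction | each patient of an observed nurse | none |
| Section VI, variables | several tied to the observed shift or the 24 hours before it | none; no later vital status needed |

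Every statement about scope is unconditional. The only conditional statement is about timing. Read together, the sections say: all assigned patients, with records read once they have left the unit. A patient who dies in the ICU has left it and has usable data for the observed shift.

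**Step 2: patients still in the ICU at the end.** The limit of 80 days in Sections V and VI applies to location and observation data. The protocol sets no closing date for record abstraction, so these patients can be abstracted later. Nothing is lost.

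**Step 3: adverse outcomes.** Section X, item 7 describes monitoring at least daily under existing hospital policy. It is not tied to the retrospective abstraction, and a daily check cannot wait for records read after the ICU stay. The transfer clause removes no deaths from it.

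**Step 4: how large would the literal reading be?** The protocol has no figure to reproduce here: it gives no ICU mortality, SOFA distribution or patient count. All inputs below are therefore assumptions.

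Let S (SOFA) and A (nursing activity) be standard bivariate normal with correlation 0.30, and let logit P(death) = c + b·S + g·A, with c solved to give the assumed mortality. The deaths are dropped and the correlation is recomputed. With b = 1.2 the odds of death rise by exp(1.2) = 3.3 per SD of SOFA. With b = 0.6 they rise by exp(0.6) = 1.8. With g = -0.4 they fall to exp(-0.4) = 0.67 per SD of activity. Results from 2,000,000 draws:

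| b | g | Mortality | Top SOFA decile lost | Shift in mean SOFA (SD) | Correlation |
|---|---|---|---|---|---|
| 1.2 | 0 | 5% | 20% | -0.06 | 0.293 |
| 1.2 | 0 | 10% | 36% | -0.10 | 0.287 |
| 1.2 | 0 | 20% | 58% | -0.20 | 0.279 |
| 1.2 | 0 | 30% | 73% | -0.29 | 0.274 |
| 1.2 | -0.4 | 10% | 33% | -0.10 | 0.315 |
| 1.2 | -0.4 | 20% | 54% | -0.18 | 0.324 |
| 1.2 | -0.4 | 30% | 68% | -0.26 | 0.331 |
| 0.6 | 0 | 10% | 22% | -0.06 | 0.296 |

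The loss in the top decile depends heavily on the assumed slope and mortality. The correlation, which is the stated aim, moves by at most about 0.03 in either direction.

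**The case for a change.** The strongest case for acting is that a timing rule that can never be met works as an exclusion. The records are used without patient consent, under a waiver. Section X gives the export to informatics specialists and has the first and every tenth case checked against IRB requirements. A careful abstractor could wait for a transfer that never comes, the patients lost would be those with the highest SOFA, and one sentence would remove the doubt.

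Part of this stands. Section III does name transfer alone and is silent on death, and applied strictly it would select on severity. Two things limit its force. The same abstractor also has Section VI, which calls for data on each assigned patient, and to omit the deaths would be to depart from that plain instruction. And Section III itself describes the patients covered without any condition, so reading the records of a patient who died fits its stated population and purpose. The further suggestion that ICU death be reported beside SOFA would add an outcome that the protocol did not plan. That is a preference, not the repair of an error.

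**Conclusion.** The concern does not hold as a defect of design. No section restricts the SOFA analysis to survivors. The label would be inexact even on the literal reading, since a patient who transfers out and dies later is still included. The points about patients still in the ICU and about adverse-event review fail on the text.

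What remains is a clerical looseness: transfer is written where the end of the ICU stay is evidently meant. If it were nonetheless applied literally, a true correlation of 0.30 would become roughly 0.27 to 0.33 under assumed mortality of 10% to 30%, with a larger loss among extreme SOFA values. Those figures rest wholly on assumed mortality, slopes and normality.

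The judgement that no change is needed rests on one further assumption: that staff follow the unconditional scope in Section VI, which is the natural way to reconcile the two sections. On that footing, clearer wording would not be expected to alter any result.

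### SOFA is called a patient outcome, but the Section VI abstraction windows give neither a full pre-shift baseline nor any post-shift value, so the planned correlation mainly reflects severity before or alongside the nursing activity

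*Protocol*

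**What the plan says.** Section I states the aim: "We will correlate nursing activity metrics against patient outcomes as measured by Sequential Organ Failure Assessment (SOFA) score". The same aim is repeated later in that section. Neither statement says when SOFA is scored.

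Section VI holds the only list of data to be taken from the patient record. SOFA itself is not on it. After background items (age, gender, diagnoses) the list gives "laboratory values occurring during, or 24 hours prior to observation time, neurological status, mean arterial pressures during observation time", then "intravenous medications administered during observation time, any diagnostic studies performed outside of the ICU during the observation time", and finally "any in-room procedures performed during the observation time".

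Section III says that patient data will be "abstracted retrospectively under the Waiver of Consent after the patients have been transferred from the ICU", and that patient factors serve to help interpret the nurse data. Section V says "The study design is prospective, observational", gives the day shift as 7:00 AM to 7:30 PM, and plans 4 months with 80 observation days. Section VI adds: "The RTLS location tag distribution and nurse observation will occur four to five days per week".

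**The concern.** A measure used as an outcome should be taken after the exposure, and in an observational study it needs a baseline taken before it. Sicker patients plausibly draw more nursing activity. If the score is built from values recorded before or during the same shift, its correlation with activity mixes severity attracting care with any effect of care on the patient. The sign may also depend on the metric chosen, for example bedside time against time at the station.

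The stake is how the SOFA result is read. Under the label of Section I it would be presented as a relation between nursing activity and patient outcome, when the listed data make it mainly a relation between nursing activity and acuity. A statistical analysis plan can choose a model and an adjustment set, but it cannot analyse values that were never abstracted. The collection windows therefore belong in Section VI of the protocol.

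**Working it through.** The protocol gives no sample size, power or effect figure for the SOFA correlation, so there is nothing of its own to reproduce. The check has three steps.

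**1. Windows.** Inputs: the Section VI list and the Section V shift hours. Assumptions: observation time is the whole shift, 07:00 to 19:30 = 12.5 h; and the listed items that would feed SOFA are laboratory values, neurological status, arterial pressure and intravenous medications (the protocol does not say which do).

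| Listed item | Before shift | During shift | After shift |
|---|---|---|---|
| Laboratory values | 24 h | 12.5 h | 0 h |
| Mean arterial pressure | 0 h | 12.5 h | 0 h |
| Intravenous medications | 0 h | 12.5 h | 0 h |
| Diagnostic studies outside the ICU | 0 h | 12.5 h | 0 h |
| In-room procedures | 0 h | 12.5 h | 0 h |
| Neurological status | no clear window | no clear window | no clear window |

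The list has 11 items, of which 5 are dated and 0 have a post-shift window. For laboratory values the span is 24 + 12.5 = 36.5 h, of which 24/36.5 = 66% is before, 34% during and 0% after. Among the dated items only laboratory values can give a baseline.

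**2. Later values that arise by chance.** If a patient is again assigned to an observed nurse on the next observed day, that day's pull adds the night (24 - 12.5 = 11.5 h) of laboratory values and the next shift's own data. The number of observed days followed by another observed day is 80 minus the number of unbroken runs of observed days, and the number of runs is at most the unobserved days plus 1. Four months is 17 to 18 weeks.

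- 17 weeks: 17 × 7 - 80 = 39 unobserved days, at most 40 runs, so at least 40 of 80 (50%).
- 18 weeks: 18 × 7 - 80 = 46 unobserved days, at most 47 runs, so at least 33 of 80 (41%).

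Later values are thus available for an appreciable but uncontrolled share of observed days, and only for patients reassigned to an observed nurse.

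**3. What timing and adjustment would each contribute.** This is an illustration on assumed coefficients, not evidence. Severity S has variance 1. Activity is A = aS + noise, with variance 1. Same-shift SOFA is W = rS + bA + noise, pre-shift SOFA is B = rS + noise (noise variance 1 - r² in both), and post-shift SOFA is P = pS + bA + noise. Grid: a = 0.2, 0.4, 0.6; r = 0.7, 0.8, 0.9; p = 0.6, 0.8. Let k = (1 - r²)/(1 - r²a²).

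- Same shift, unadjusted: correlation (ra + b)/√(1 + b² + 2abr). With b = 0 it runs from 0.14 to 0.54, although nursing has no effect.
- Same shift, adjusted for B: coefficient b + rak.
- Post-shift, unadjusted: b + pa.
- Post-shift, adjusted for B: b + pak.

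Cells with the wrong (positive) sign when the true effect is a benefit:

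| Analysis | b = -0.1 | b = -0.2 |
|---|---|---|
| Same shift, unadjusted | 9 of 9 | 6 of 9 |
| Post-shift, unadjusted | 18 of 18 | 12 of 18 |
| Same shift, adjusted | 5 of 9 | 2 of 9 |
| Post-shift, adjusted | 8 of 18 | 3 of 18 |

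Moving the score after the shift gains nothing by itself in this model; nearly all the gain comes from the baseline. Adjustment removes 1 - k of the confounding, from 38% (r = 0.7, a = 0.6) to 80% (r = 0.9, a = 0.2). It can still fail: at a = 0.6, r = 0.9, p = 0.8, b = -0.1, the result is -0.1 + 0.48 × 0.19/0.7084 = +0.03.

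**The case against.** The strongest reply is that the protocol promises only a correlation in an observational study. Section III gives patient data an interpretive role, for which same-shift windows are suitable, and the mention of improved patient outcomes in Section VIII concerns future workflow management. This stands to a large extent. A reader might infer that the study set out to show that nursing activity changes patient outcome and cannot; the documents do not support that, because no causal aim is stated. What remains is that Section I twice calls SOFA an outcome while the listed windows do not yield one.

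A second reply is that adjustment is an analysis choice for the statistical analysis plan, and that some time order is already available: prior-24 h laboratory values against the shift, or late-shift laboratory values and pressures against earlier activity. This stands in part. The order is incomplete, because pressures and intravenous medications have no pre-shift value.

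A third is that post-shift timing is not shown to be better. A reader might infer that abstracting SOFA after the shift would by itself cure the problem; the illustration shows no such gain. The 24 h after the shift also lie wholly under later care (11.5 h night, 12.5 h next day). If that halved a true -0.2 to -0.1, the adjusted post-shift sign would be wrong in 8 of 18 cells, against 2 of 9 for same-shift SOFA adjusted for baseline with the effect acting fully in the shift. This stands, so the sign counts are no argument for post-shift timing. The case for a later value is one of definition: a score to be reported as an outcome of the activity should follow it.

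A fourth is that consecutive observed days supply later values. They do, on at least 41% to 50% of observed days within the stated 4 months. A reader might infer a floor of 24% (19 of 80), but that needs 20 weeks at four days a week, beyond the duration in Section V. These values are still incidental, not planned.

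Finally, the list may not be exhaustive. That is possible, but no other source or time for SOFA is given.

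**Conclusion.** The point holds in a limited form. By the stated windows, the listed data support neither a full pre-shift baseline SOFA nor a SOFA measured after the activity: 0 of 5 dated items extend past the shift and 1 of 5 reaches back before it. The correlation, followed as written, mainly reflects severity before or alongside the activity and should not be reported as an outcome result.

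The window count rests on the text alone. The hours assume that observation spans the whole day shift. The importance of pressures, intravenous medications and neurological status assumes that they feed the score. The size of any confounding is unknown; the 0.14 to 0.54 range depends entirely on assumed correlations and on activity rising with severity.

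Only the SOFA objective is affected. Validation of the location system against manual observation (5% maximum error), the location metrics and the control chart are untouched. The point is worth correcting before records are pulled. Confidence is medium.

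**What to change.** In Section VI, abstract all SOFA components for every observed patient-shift in a fixed pre-shift window (for example the 24 h before 07:00) and a fixed post-shift window (for example the 24 h after 19:30, with 19:30 to 07:00 as a sensitivity window), whether or not the later day is observed and whoever is then assigned. Give neurological status a window. Analyse later SOFA on activity adjusted for pre-shift SOFA, with a stated analysis rule for deaths and ICU discharges, and report the same-shift correlation as association with acuity. If only one window can be added, the illustration favours the pre-shift baseline, but the score should then not be called an outcome following the activity.

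If the windows are not widened, relabel SOFA in Section I as a concurrent severity measure. That costs one sentence and gives up SOFA as an outcome.

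Widening costs protocol wording, a longer date range in a record pull that already takes place after ICU transfer, and probably an IRB amendment, since abstraction runs under the Waiver of Consent. It needs no extra patients, visits or observers. The drawbacks are missing post-shift values after ICU discharge or death, dilution by later care, and residual confounding (0.02 to 0.30 SD in the illustration).
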